5.4 Definition of Dose Limiting Toxicity (DLT)

A significant reduction of total IgG levels in serum is a desired effect of IdeS treatment and is not considered a DLT. Any novel AE (including infusion reactions) with a Common Toxicity Criteria for Adverse Events (CTCAE) v.4.0 grade 3 or more and with a possible relationship to the investigational drug is considered a DLT (see Appendix 1 for CTCAE v. 4.0).

5.5 Internal Monitoring Committee

An IMC will be formed and will be convened to assess safety data on each patient enrolled in the study. If at any time in the study, 2 or more patients have experienced a Grade 3 of related adverse event (NCI CTCAE v 4.0), the IMC will be convened. The IMC will also review a safety data package (Table 3) prior to dose escalation. An IMC charter will be written to pre-specify roles, responsibilities, procedures, and deliverables, as well as the purpose, scope, and timing of meetings.

6. PATIENT SELECTION CRITERIA

6.1 Study Population

6.1.1 Inclusion Criteria

For inclusion in the study patient must fulfil the following criteria.

1. Ability to understand and must sign the informed consent form
2. Age 18 years or above
3. Patients diagnosed with acquired TTP with ADAMTS13 levels of $\leq 10\%$ in clinical remission and with measurable or previously confirmed ADAMTS13 antibodies
4. Females of childbearing potential and males must use highly effective contraception during the study and at least for 12 weeks after IdeS dosing

Highly effective contraception methods include:

1. Total abstinence (when this is in line with the preferred and usual lifestyle of the subject. Periodic abstinence (e.g., calendar, ovulation, symptothermal, post-ovulation methods) and withdrawal are not acceptable methods of contraception
2. Female sterilisation (have had surgical bilateral oophorectomy with or without hysterectomy) or tubal ligation at least six weeks before taking study treatment. In case of oophorectomy alone, only when the reproductive status of the woman has been confirmed by follow up hormone level assessment
3. Male sterilisation (at least 6 months prior to screening). For female subjects in the study, the vasectomised male partner should be the sole partner for that subject
4. Combination of any two of the following methods (a+b or a+c or b+c):
 - a) Use of oral, injected or implanted hormonal methods of contraception or other forms of hormonal contraception that have comparable efficacy (failure rate $<1\%$), for example hormone vaginal ring or transdermal hormone contraception
 - b) Placement of an intrauterine device (IUD) or intrauterine system (IUS).
 - c) Barrier methods of contraception: condom or occlusive cap (diaphragm or cervical/vault caps) with spermicidal foam/gel/film/cream/vaginal suppository

In case of use of oral contraception women should have been stable on the same pill for a minimum of 3 months before taking study treatment. Women are considered post-menopausal and not of child bearing potential if they have had 12 months of natural (spontaneous) amenorrhea with an appropriate clinical profile (e.g., age appropriate, history of vasomotor symptoms) or have had surgical bilateral oophorectomy (with or without hysterectomy) or tubal ligation at least six weeks prior to screening. In the case of oophorectomy alone, only when the reproductive

status of the woman has been confirmed by follow up hormone level assessment is she considered not of child bearing potential.

6.1.2 Exclusion Criteria

Patients must not enter the study if any of the following exclusion criteria are fulfilled

1. Prior malignancy within 5 years excluding adequately treated basal cell or squamous cell skin cancer, cervical carcinoma in situ
2. Any positive result on screening for serum hepatitis B surface antigen, hepatitis C antibody and HIV
3. Clinical signs of ongoing infectious disease. This includes P-C-reactive protein (CRP) >10.
4. Tested positive for IgE antibodies against IdeS as measured by ImmunoCap.
5. No secondary cause of TTP
6. Rituximab treatment or other antibody-based therapy within 7 days prior to IdeS dosing
7. Treatment with investigational medicinal product within the last 12 weeks preceding screening or longer if judged by the investigator to possibly influence the outcome of the current study
8. Severe other conditions requiring treatment and close monitoring, e.g. cardiac failure \geq NYHA (New York Heart Association) grade 3, unstable coronary disease or oxygen dependent COPD
9. History of any other clinically significant disease or disorder which, in the opinion of the investigator, may either put the patient at increased risk because of participation in the study, or influence the results or the patient's ability to participate in the study
10. Hypogammaglobulinemia defined as any values of P-total IgG less than 3 g/L
11. History of severe allergy/hypersensitivity or ongoing allergy/hypersensitivity, as judged by the investigator or history of hypersensitivity to drugs with a similar chemical structure or class to IdeS (e.g., streptokinase and/or staphylokinase)
12. Substance abuse or other concurrent medical condition that, in the investigator's opinion, could confound study interpretation or affect the patient's ability to tolerate or complete the study
13. Investigator considers patient unlikely to comply with study procedures, restrictions and requirements
14. Breast feeding women or women with a positive pregnancy test
15. Previously received IdeS treatment

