3. INTRODUCTION

3.1 Disease and Patient population

Thrombotic thrombocytopenic purpura (TTP) is a rare life-threatening thrombotic disorder of the blood-coagulation system, causing extensive microscopic clots to form in the small blood vessels throughout the body. These small blood clots, called thrombi, can damage many organs including the kidneys, heart and brain. TTP is a medical emergency that is almost always fatal if appropriate treatment is not initiated promptly. Treatment with plasma exchange (PE) and glucocorticoids reduces the mortality to between 10% and 15% (George 2012).

In the majority of patients, TTP is a result of autoantibody-mediated inhibition of a disintegrin and metalloproteinase with a thrombospondin type 1 motif, member 13 (ADAMTS13). This type of TTP is called acquired TTP. In a minority of patients, TTP is due to deleterious mutations in ADAMTS13; i.e., hereditary or congenital TTP.

Acquired TTP is characterized by thrombocytopenia and microangiopathic haemolytic anemia (MAHA) without an obvious cause, and may include fever, mild renal failure, and neurologic deficits (Sayani and Abrams 2015). The majority of the patients suffering from acquired TTP develop autoantibodies that bind and neutralize the proteolytic activity of ADAMTS13 and/or accelerate its clearance *in vivo* (Scheiflinger, Knöbl et al. 2003). Recently published data suggest that depletion of ADAMTS13 antigen, rather than enzyme inhibition, is the dominant pathogenic mechanism in acquired TTP (Thomas, de Groot et al. 2015). A severe deficiency of plasma ADAMTS13 activity (less than 5%) and the presence of autoantibodies are considered to be highly specific for the diagnosis of acquired TTP (Hovinga and Lämmle 2012). Anti-ADAMTS13 antibodies are present in the majority of patients (94–97%) suffering from acquired TTP and are considered to be strongly involved in the pathogenesis of the disease (Verbij, Fijnheer et al. 2014).

Early intervention improves prognosis dramatically. As a result, measurement of serum ADAMTS13 activity is not performed for diagnosis, as turn-around time tends to be long and awaiting results may delay life-saving treatment. However, measurement of ADAMTS13 and antibodies to ADAMTS13 are conducted for diagnostic confirmation.

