4. STUDY OBJECTIVES AND ENDPOINTS

4.1 Objectives

4.1.1 Primary Objective

To assess safety and tolerability of single intravenous doses of IdeS in patients diagnosed with asymptomatic antibody-mediated TTP with low ADAMTS13 activity

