5. STUDY DESIGN

5.1 Overall Study Design

[figure not shown]

Figure 1. Overall schematic study design

This is a phase II, single arm study. The primary objective of the study is to assess safety and tolerability of IdeS in asymptomatic patients diagnosed with acquired TTP in clinical remission with ADAMTS13 activity less than 10% of normal levels. Secondary objectives include monitoring of ADAMTS13 activity and levels of ADAMTS13 antibodies. In addition, IdeS serum concentration, PD (total IgG and F(ab')₂ fragment concentrations) and immunogenicity profile of IdeS will be assessed.

Patients will be treated at the College University London Hospital, and will be subject to a single 30 minutes infusion with IdeS on day 0. Blood sampling for safety and efficacy will be performed and the patient will be closely monitored over a 24 h period after infusion after which they will be discharged. The follow-up visits will be in the out-clinic setting. Patients will receive premedication with paracetamol, Solu-Medrol and Loratidine before IdeS infusions. All patients will also receive a two-week regimen of prophylactic antibiotics starting pre-dose.

Following an evaluation of safety (clinical chemistry, haematology and coagulation and AEs) and efficacy in 3 patients receiving 0.25 mg/kg there will be a potential to increase the IdeS dose to 0.5 mg/kg for the remaining 3 patients.

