7.2 Study Procedures

For each patient the duration of the treatment period including screening and follow up visits will be approximately 3 months. Timing (45 min, 2 h, 6 h and 24 h respectively as indicated in the flow chart in Table 2) of sampling on day 0 relates to start of infusion.

Visit 1 (Screening Day -28 – 4)

All patients considered for the study must give their written consent before screening or any other study procedure is performed. Screening of a patient can take place up to 28 days before the first dosing on study day 0. To be eligible for the study patients have to meet all inclusion criteria and no exclusion criteria. A patient failing screening may not be rescreened. However, if a patient has been screened and found eligible he or she can be rescreened if dosing could not be performed within 28 days due to logistical reasons.

At the screening visit each subject will be informed about the study and after signing the informed consent form assessments for eligibility will commence. The eligibility evaluation includes adherence to inclusion and exclusion criteria, collection of concomitant medication, demographic data and medical history. A full physical examination, height and weight measurements, vital signs including resting blood pressure, pulse, respiratory frequency, 12-lead resting ECG and body temperature will be measured. AEs that occur in the time period between informed consent and administration of the trial drug should be recorded as part of the patient's medical history, but will not be considered a treatment emergent adverse event (TEAE) unless directly related to study procedures (e.g., hematoma secondary to laboratory testing) or it meets the definition of an SAE.

Additionally, blood sampling for serology (HIV, hepatitis), pregnancy test, clinical chemistry (including [REDACTED] and immunoglobulins), haematology (including [REDACTED])

and urine sampling for urinalysis as well as blood samples for analysis of ADAMTS13 activity, ADAMTS13 antibodies, and anti-IdeS IgE will be collected.

Visit 2 (Residential stay Day 0 to Day 1)

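### Exclusion criterion 5 is inverted as written: it bars patients without a secondary cause of TTP and does not itself bar patients with one

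*Protocol*

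**What the plan says.** Protocol 6.1.2 opens its list of 15 items with this rule: "Patients must not enter the study if any of the following exclusion criteria are fulfilled". Item 5 on the list is "No secondary cause of TTP". Protocol 7.2, under the screening visit, states the same logic again: "To be eligible for the study patients have to meet all inclusion criteria and no exclusion criteria".

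The inclusion list in 6.1.1 works the other way round. Its lead-in is "For inclusion in the study patient must fulfil the following criteria". Inclusion item 3 concerns acquired TTP in remission and does not mention secondary causes.

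The nearest the protocol comes to describing cause is in the introduction, section 3.1: "Acquired TTP is characterized by thrombocytopenia and microangiopathic haemolytic anemia (MAHA) without an obvious cause".

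The SAP does not restate the eligibility criteria. Its introduction and section 2 record that the trial was terminated after two patients had been treated.

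**The concern.** An exclusion list works only if each item names something that keeps a patient out. Item 5 names something that appears to be a condition for getting in. Under its lead-in, the item does the reverse of what a reader would expect.

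This is an operative rule. Eligibility is assessed at screening and again within the hour before infusion (7.2). Incorrect enrolment is a listed reason for discontinuation (6.3.1), and any replacement patient must be eligible under the protocol. A site that follows the text turns away patients without a secondary cause. A site that follows the probable intent departs from the text. In either case the eligibility record is ambiguous, and protocol 12.4 expects issues from the review of violations to be settled before the database is locked.

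**Working it through.** No figure in the plan bears on this point, so the check is a logical reading of the item under its lead-in, followed by a count.

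**Rule.** From 6.1.2 and 7.2: a patient is eligible if every inclusion statement is true and no exclusion statement is true.

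**Item 5 under that rule.**

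| Patient | Is the item 5 statement true? | Result from item 5 |
|---|---|---|
| Without a secondary cause | Yes, so the criterion is fulfilled | Barred |
| With a secondary cause | No, so the criterion is not fulfilled | Not barred by this item |

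**The same words under the 6.1.1 lead-in.** There a true statement is required for entry. A patient without a secondary cause would pass and a patient with one would fail. The phrase is coherent in that list and inverted in the list where it stands.

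**Comparison with the other items.** Items 1 to 4 (4 items) and 6 to 15 (10 items) each name a condition, finding, treatment or judgement whose presence bars entry: 4 + 10 = 14. That leaves 15 − 14 = 1 item worded as an absence, item 5.

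**Does another provision cure it?**
- Items 9 and 12 are worded generally and rest on the investigator's opinion. They could keep out some patients with a secondary cause, but neither is a rule on secondary TTP.
- No item can re-admit a patient whom item 5 bars, because one fulfilled exclusion is enough.
- Inclusion item 3 neither requires nor rules out a secondary cause.
- The term appears once in the text available for review, in item 5 itself, and is not defined there or elsewhere. Some pages were removed before review, so this statement covers only the text supplied.

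**Comparison with the described disease.** Section 3.1 describes acquired TTP as arising with no evident cause. Literal item 5 bars patients with no secondary cause. If the two expressions mean roughly the same thing, the rule bars the patients the introduction describes.

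**The case against.** The strongest reply is that this is a slip nobody would act on. An experienced single site would read item 5 as intended. The trial has stopped, the SAP introduction says the sponsor will not pursue the indication, and so an amendment or reuse is hypothetical. Medical history will be listed, all recorded data are to be presented (SAP 3 and 4.2), and violations are reviewed before lock, so much of what a reader needs may already be available. Most of this stands, and it limits the weight of the point. It does not make the text right, and none of those provisions guarantees a statement on how item 5 was applied.

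A second reply is that the conflict with the rest of the protocol is thin. This also largely stands. A reader might infer that the objective ("patients diagnosed with asymptomatic antibody-mediated TTP with low ADAMTS13 activity"), the design section ("asymptomatic patients diagnosed with acquired TTP in clinical remission with ADAMTS13 activity less than 10% of normal levels") and inclusion item 3 ("Patients diagnosed with acquired TTP with ADAMTS13 levels of" and so on) contradict item 5 outright. They do not: none says that acquired or antibody-mediated TTP excludes a secondary cause, and 3.1 contrasts acquired TTP with the hereditary form, not with secondary TTP. Only the remark in 3.1 about the lack of an obvious cause helps. That remark is background description, and its grammar lets it attach to the thrombocytopenia and anaemia. The firm basis for the point is therefore item 5 read under its own lead-in.

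**Conclusion.** The point holds as a drafting inversion in an operative eligibility rule. As written, item 5 gives a result opposite to its probable purpose, and nothing in the available text corrects it. The literal reading needs no assumption beyond the lead-in. The intended reading is a strong inference from three things: the item's form, the fact that it works in the other list, and 3.1. It is not a stated fact.

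The size is small. One of 15 exclusion items is affected, and 2 of 6 planned patients were treated. SAP 3 defines no analysis sets and SAP 5 plans no efficacy section, so no planned listing or plot changes.

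A reader might go further and infer that the two treated patients were wrongly enrolled. Read literally, each of them either had a secondary cause or fulfilled item 5. That follows from the wording alone and says nothing about whether either patient was unsuitable. The documents do not report how the item was applied, and no mis-enrolment is shown. Nor do they support the inference that patients with a secondary cause had open entry, since items 9 and 12 leave room to keep some of them out.

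**What to change.** In any amendment or reuse of the protocol, reconcile item 5 with the 6.1.2 lead-in. Either delete the word *No*, so that the item names the condition that bars entry, or move the line unchanged to 6.1.1. The sponsor should confirm which meaning was intended. If the criteria are reused, the sponsor should also say what counts as a secondary cause, because the reworded item would otherwise still rest on an undefined term.

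In the abbreviated report, add one sentence stating how item 5 was read and applied for the two treated patients.

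The cost is one word or one moved line in the protocol, a short definition if it is reused, and one sentence in the report. Sample size, visits, assays and planned data presentations are unaffected.

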6.2 Restrictions

Patients should abstain from drinking alcoholic beverages for 72 hours before the screening visit and all subsequent visits to the clinic. In addition, patients should abstain from alcoholic beverages during the residential stay.

The patients should abstain from strenuous physical activity that is not within the patient's normal weekly routine for 48 h prior to any visit until the end of study.

Patients must not participate in another clinical study during the course of the present study.

6.3 Withdrawal and Discontinuation

6.3.1 Criteria for Discontinuation from the Study

Patients may be discontinued from study treatment and assessments at any time. Specific reasons for discontinuation can be:

- Voluntary discontinuation by the patient who is at any time free to discontinue his/her participation in the study, without prejudice to further treatment
- Risk to patients as judged by the investigator and/or sponsor
- Severe non-compliance to protocol as judged by the investigator and/or sponsor
- Incorrectly enrolled patients
- Patient lost to follow-up
- Adverse events
- Withdrawal of informed consent to the use of biological samples may be a reason for withdrawal of a patient

Patients who are withdrawn from the study by the investigator due to adverse events will not be replaced. Patients who withdraw for reasons other than adverse events may be replaced. A replacement patient must be an eligible patient according to the protocol and inclusion will follow the procedures described in this protocol.

6.3.2 Procedures for Discontinuation of a Patient from the Study

A patient who discontinues after study drug administration will always be asked about the reason(s) for discontinuation and the presence of any adverse events. If possible, they will be seen and assessed by an investigator(s). Adverse events will be followed until they resolve, stabilize or the clinical outcome of the patient is ascertained. If possible, patients who discontinue from the study before completion should undergo the assessments and procedures scheduled for the end of study follow up visit. Patients who, for a medical reason, cannot comply with the protocol procedures will be followed by best procedure, e.g., telephone call, to retrieve safety and efficacy data.

2. Deliveries are recorded
3. Study treatments are handled and stored safely and properly
4. The study drug provided for this study will be used only as directed in the study protocol
5. The study personnel will account for all drugs dispensed and returned. Any discrepancies must be documented, investigated and appropriately resolved
6. At the end of the study, the pharmacy personnel will account for all unused drugs and for appropriate destruction/return of all unused drugs to the sponsor for destruction. Certificates of delivery, destruction and return must be signed by a study team member.

7.1.5 Administration of IMP

An intravenous dose of IdeS will be administered over 30 minutes. Each patient will receive a single dose of 0.25 or 0.5 mg/kg BW. Detailed instructions on preparation and administration are provided in the pharmacy manual. The infusion may be slowed down or stopped and restarted if required.

7.2 Study Procedures

For each patient the duration of the treatment period including screening and follow up visits will be approximately 3 months. Timing (45 min, 2 h, 6 h and 24 h respectively as indicated in the flow chart in Table 2) of sampling on day 0 relates to start of infusion.

Visit 1 (Screening Day -28 – 4)

All patients considered for the study must give their written consent before screening or any other study procedure is performed. Screening of a patient can take place up to 28 days before the first dosing on study day 0. To be eligible for the study patients have to meet all inclusion criteria and no exclusion criteria. A patient failing screening may not be rescreened. However, if a patient has been screened and found eligible he or she can be rescreened if dosing could not be performed within 28 days due to logistical reasons.

At the screening visit each subject will be informed about the study and after signing the informed consent form assessments for eligibility will commence. The eligibility evaluation includes adherence to inclusion and exclusion criteria, collection of concomitant medication, demographic data and medical history. A full physical examination, height and weight measurements, vital signs including resting blood pressure, pulse, respiratory frequency, 12-lead resting ECG and body temperature will be measured. AEs that occur in the time period between informed consent and administration of the trial drug should be recorded as part of the patient's medical history, but will not be considered a treatment emergent adverse event (TEAE) unless directly related to study procedures (e.g., hematoma secondary to laboratory testing) or it meets the definition of an SAE.

Additionally, blood sampling for serology (HIV, hepatitis), pregnancy test, clinical chemistry (including [REDACTED] and immunoglobulins), haematology (including [REDACTED])

and urine sampling for urinalysis as well as blood samples for analysis of ADAMTS13 activity, ADAMTS13 antibodies, and anti-IdeS IgE will be collected.

Visit 2 (Residential stay Day 0 to Day 1)

Patients found eligible at the screening visit will be included in the study. At visit 2 an eligibility check will be performed pre-dose within 60 min prior to IdeS infusion (inclusion/exclusion criteria, medical history, concomitant medication, vital signs, body temperature, urinalysis, blood sampling for pregnancy test, safety laboratory parameters (including [REDACTED], [REDACTED] and immunoglobulins (IgG, IgM and IgA), ADAMTS13 activity, ADAMTS13 antibodies, [REDACTED], IdeS concentration, total IgG and F(ab')₂ fragment concentrations (PD) and ADA. Hydrocortison, paracetamol and antihistamine (chlorphenamine maleate) will be administered pre-dose to prevent/minimise risk of infusion reactions. Weight will be measured and prophylactic antibiotics will be administered.

Patients will receive a single intravenous dose of IdeS over 30 minutes.

At 2, 6 and 24 h post IdeS infusion blood sampling for determination of total IgG and F(ab')₂ fragment concentrations (PD), ADAMTS13 activity and antibodies, safety laboratory parameters, body temperature and [REDACTED] as well as urine sampling will be performed. Assessment of vital signs and ECG will be performed at 6 hours post dosing.

At 45 min, 2, 6 and 24 h post IdeS infusion sampling for determination of IdeS concentration will be performed.

AEs and concomitant medication will be recorded on the applicable CRFs throughout the visit.

Visit 3, 4, 5 and 6 (Days 3, 7, 10 and 14 respectively)

At visits 3, 4, 5 and 6 safety laboratory parameters, IdeS concentration, total IgG and F(ab')₂ fragment concentrations (PD), AEs and concomitant medication will be assessed as well as vital signs, ADAMTS13 activity, ADAMTS13 antibodies and [REDACTED]. Urine will be collected for urinalysis. Additionally, at visits 3, 4 and 6 ADA will be measured. Body temperature, weight and 12-lead resting ECG will only be measured at visit 6.

Visit 7 (Day 30)

At visits 7 safety laboratory parameters, total IgG and F(ab')₂ fragment concentrations (PD), AEs and concomitant medication will be assessed as well as vital signs, weight, body temperature, 12-lead resting ECG, ADAMTS13 activity, ADAMTS13 antibodies and [REDACTED]. A physical examination will be performed. Urine will be collected for urinalysis.

Visit 8 (End of Study, Day 64)

A follow-up visit will be performed 64 days following IdeS infusion. This will be considered the end of study for the patient. At this visit a physical examination will be performed and the patient will be assessed for vital signs, weight, body temperature, 12-lead resting ECG, AEs and concomitant medication. Blood sampling for analysis of safety laboratory

parameters, pregnancy test, ADAMTS13 activity, ADAMTS13 antibodies, [REDACTED], total IgG and F(ab')₂ fragment concentrations (PD) and anti-drug antibody (ADA) will be performed. Urine will be collected for urinalysis.

